10.12 Intellectual Property

During the term of this trial and thereafter, Institution, its employees, agents, subcontractors or affiliates will not disclose confidential information (other than to Merck KGaA or Merck KGaA designated parties) without Merck KGaA's prior written consent.

"Confidential information" will include the protocol, eCRFs, and all materials and information concerning Merck KGaA and the trial disclosed to the Institution or Investigator by Merck KGaA or developed as a result of conducting the trial, except any portion thereof which:

- · Is known to Institution, its employees, agents, subcontractors or affiliates before receipt thereof under this protocol, as evidenced by its written records;
- · Is disclosed to Institution, its employees, agents, subcontractors or affiliates after acceptance of this protocol by a third party who has a right to make such disclosure in a non-confidential manner; or
- · Is or becomes part of the public domain through no fault of the Institution, its employees, agents, subcontractors or affiliates.
- Nothing in this trial will be construed to restrict the Institution or Investigator from disclosing confidential information as required by law or court order or other regulatory order or request, provided in each case the party requested to make such disclosure will timely inform Merck KGaA and use all reasonable efforts to limit the disclosure and maintain the confidentiality of such confidential information to the extent possible. In addition, the disclosing party will permit Merck KGaA to attempt to limit such disclosure by appropriate legal means.
- Further, during the term of this protocol and thereafter, the Institution, its employees, agents, subcontractors or affiliates will not use the confidential information for any purpose other than that indicated in this protocol and the clinical research agreement without Merck KGaA's prior written approval.
- · Institution, its employees, agents, subcontractors or affiliates will not disclose to Merck KGaA any information which is confidential or proprietary to a third party unless Institution has first obtained the prior written approval of both such third party and Merck KGaA.

10.13 Trial or Site Discontinuation

Protocol Version: 3.0 / Jan 31, 2018 46 / 49

trial

· At any time of the study, due to adverse events, or risks outweighing the benefit as determined by the investigators;

Merck KGaA may temporarily or permanently discontinue the trial at a single site or at all sites for ethical, compliance or other reasons. If this is necessary, Merck KGaA will endeavor to provide advance notification to the site. If the site or trial is suspended or discontinued, the Investigator will be responsible for ensuring prompt notification to the EC. Where required by local regulations, Merck KGaA will be responsible for informing the EC of trial or site discontinuation.

10.14 Trial Closure

Upon completion (when all subjects enrolled have completed the ongoing pregnancy ultrasound test or have previously exited the trial, and the eCRFs and queries have been completed) or termination of the trial, Merck KGaA will notify the sites.

Close-out activities will be performed. The GERI+ system and any unused trial material will be collected and returned to Merck KGaA and/or the CRO. The monitors (CRO) will ensure that the investigator's regulatory files are up to date and complete, that printed CRFs are provided as PDF files to the sites, and that any outstanding issues from previous visits have been resolved. Other issues that may be reviewed with the investigator include: discussing record retention requirements (refer to the Section on Investigator Records), publication policy, and notifying the EC of trial closure, etc.

#### 2 List of Abbreviations and Definition of Terms

ADR Adverse Drug Reaction

AE Adverse Event

AFC Antral Follicle Count

AMH Anti-Mullerian Hormone

ART Assisted Reproductive Technologies

BMI Body Mass Index

COS Controlled Ovarian Stimulation

CRF Case Report Form

CSR Clinical Study Report

EEVA Early Embryo Viability Assessment

(FA) dataset Full Analysis dataset

FPI First Patient In

FSH Follicle-Stimulating Hormone

GERI+ Genea Embryo Review Instrument Plus

GnRH Gonadotropin Releasing Hormone

hCG Human Chorionic Gonadotropin

IAP Integrated Analysis Plan

ICF Informed Consent Form

ICH International Council for Harmonization

ICSI Intra cytoplasmic Sperm Injection

IHC Internationally Harmonized Consensus

IVF In Vitro Fertilization

LH Luteinizing Hormone

LPI Last Patient In

LPO Last Patient Out

(PP) dataset Per Protocol dataset

POR Poor Ovarian Response

r-hFSH Recombinant Human Follicle-Stimulating Hormone

r-hLH Recombinant Human Luteinizing Hormone

SAE Serious Adverse Event

SAS Statistical Analysis System

SD Standard Deviation

SmPC Summary of Product Characteristics

# **3** Modification History

Unique Identifier for Version	Date of IAP Version	Author	Changes from the Previous Version
0.1	16APR2018	PPD	Baseline Version
0.2	19JUN2018	PPD	Based on Client comments
0.3	17JAN2019	PPD	Based on Client comments
0.4	12FEB2019	PPD	Based on client comments
1.0	14FEB2019	PPD	Final Version
1.1	09DEC2019	PPD	Based on Client suggestions
2.0	14JAN2020	PPD	Final Version

# 4 Purpose of the Integrated Analysis Plan

The purpose of this Integrated Analysis Plan (IAP) is to document technical and detailed specifications for the final analysis of data collected for protocol MS200497\_0006. Results of the analyses described in this IAP will be included in the Clinical Study Report (CSR). Any post-hoc, or unplanned analyses performed to provide results for inclusion in the CSR but not identified in this prospective IAP will be clearly identified in the CSR.

The IAP is based upon the trial protocol and is prepared in compliance with ICHE9. This IAP is mainly focused on the Clinical pregnancy with positive fetal heart beat in gestational week 6-8 after fresh embryo transfer on Day 3. Statistical analyses of other variables such as Utilizable Embryos, Good Quality Embryos, Non-viable Embryos and Implantation with positive fetal heart beat, Biochemical Pregnancy, Ongoing Pregnancy, Multiple Pregnancy, Ectopic Pregnancy and Spontaneous Miscarriage also added in this version of IAP.

# **5** Objectives and Endpoints

	Objective	Endpoint	IAP section
Trial Objective	The main aim of this trial is to evaluate the overall clinical value of GERI+ as an integrated embryo culture and assessment system, providing an undisturbed culture environment, continuous monitoring of embryo development and automated scoring using a predictive algorithm	Primary Endpoint Clinical pregnancy with positive fetal heart beat in gestational week 6-8 after fresh embryo transfer on Day 3.	14.1
		Secondary Endpoints  1. Number of utilizable embryos  2. Number of good quality embryos  3. Number of non-viable embryos  4. Implantation with positive fetal heart beat  5. Biochemical pregnancy  6. Ongoing pregnancy  7. Multiple pregnancy  8. Ectopic pregnancy  9. Spontaneous miscarriage	14.2

#### **6** Overview of Planned Analyses

This IAP describes final analysis of the study. No interim analyses are planned for this study.

#### 6.1 Interim Analysis

Not applicable.

#### 6.2 Final Analysis

Final analyses will be performed only after the database locked. In addition, no database can be locked and no randomization code should be unblinded until this IAP has been approved.

# 7 Changes to the Planned Analyses in the Clinical Trial Protocol

The statistical methods as described in the protocol were adopted and no changes to the planned analyses. However Statistical comparison between groups and confidence intervals will not be performed. No regression models will be constructed in this study.

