6.11 Potential Confounding Factors

Smoking status, age, gestational history, COS strategy, embryo culture media, luteal phase support, number of embryos transferred and site locations are potential confounding factors in this study. Multivariate logistic analysis will be performed with these factors in the model as covariates when testing the primary endpoint.

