8. STATISTICS

8.1 Sample Size

Based on an expected clinical pregnancy rate of 30% (Adamson et al., 2016) in the control group and a 25% relative increase of clinical pregnancy rate in the experimental group, a two-sided test with an alpha level of 0.05 needs 623 subjects per group to reach a power of 80%. With a drop-out rate of 10%, 1,386 subjects (693 per group) need to be randomized. A subject can be considered as a drop-out during the study if she is randomized but primary endpoint data is not available for this subject, for whatever reason.

The calculation of sample sizes was performed using nQuery Advisor® version 7.0.

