8.4.2 Analysis of Primary Endpoint

The FHB positive clinical pregnancy rate (the number of subjects with FHB positive clinical pregnancy divided by the number of subjects with embryo transfer) for either of the two treatment groups will be computed.

Primary hypothesis will be tested between the treatment groups based on a Cochrane-Mantel-Haenzel CMH test adjusting for stratification factors providing the derived Odds Ratio and its 95% confidence interval. As sensitivity analysis, a logistic regression model with confounding factors and stratification factors as covariates will be performed. Details regarding the model and analysis will be specified in the SAP.

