#### 14 Efficacy Analyses

# 14.1 Clinical Pregnancy with positive fetal heartbeat (Primary Endpoint)

The primary end point is clinical pregnancy with positive fetal heartbeat. It is defined as the pregnancy diagnosed by ultrasonographic or clinical documentation of at least one fetus with heart beat in gestational week 6 to 8. It includes ectopic pregnancy.

The qualitative variables

- Ultrasound performed (Yes/No)
- Result of ultrasound (Biochemical pregnancy/ Ectopic pregnancy/ Intrauterine clinical pregnancy (with and without positive FHB)/ Clinical pregnancy (FHB positive or negative intrauterine pregnancy + ectopic pregnancy)/ Other)
- Number of subjects with Embryo transfer attempted (Yes/No)
- Subjects with FHB positive clinical pregnancy

will be summarized by using number and percentage for both treatment groups and overall from (FA) dataset and (PP) dataset.

The quantitative variables

- Number of intrauterine gestational sacs
- Number of sacs with fetal heartbeats

will be summarized by using descriptive statistics for both treatment groups and overall from (FA) dataset and (PP) dataset.

The quantitative variable

• FHB positive Clinical pregnancy rate (%)

will be summarized by percentage for both treatment groups and overall from (FA) dataset and (PP) dataset.

No. of subjects with clinical pregnancy = Intrauterine clinical pregnancy subjects (with and without positive FHB) + Ectopic pregnancy subjects.

**Subject with FHB positive clinical pregnancy** = Intrauterine Clinical Pregnancy subject with at least one or more sacs with fetal heartbeats

FHB positive clinical pregnancy rate (%) = No. of subjects with FHB positive clinical pregnancy)/ No. of subjects with embryo transfer)\* 100.

No. of subjects with embryo transfer = Subjects with embryo transfer attempted.

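### SAP section 7 declares no changes to the planned analyses, then cancels the protocol's primary CMH test, its confidence interval and the logistic model, with no reason given in the visible text

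*SAP*

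**What the plan says.** **Protocol.** Section 8.4.2 says: "Primary hypothesis will be tested between the treatment groups based on a Cochrane-Mantel-Haenzel CMH test adjusting for stratification factors", with an odds ratio and its 95% confidence interval. It adds a logistic regression on confounding and stratification factors as a sensitivity analysis and leaves the details to the SAP. Section 6.11 lists the potential confounders and adds: "Multivariate logistic analysis will be performed with these factors in the model as covariates when testing the primary endpoint". Section 8.1 takes 30% in the control arm and a 25% relative increase, and states that "a two-sided test with an alpha level of 0.05 needs 623 subjects per group to reach a power of 80" per cent. With 10% drop-out this becomes 693 per arm, 1,386 in total.

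**SAP.** Section 7, the place for departures from the protocol, opens with: "The statistical methods as described in the protocol were adopted and no changes to the planned analyses". It continues directly: "However Statistical comparison between groups and confidence intervals will not be performed. No regression models will be constructed in this study". For the primary endpoint, section 14.1 says that the FHB-positive clinical pregnancy rate "will be summarized by percentage for both treatment groups and overall from (FA) dataset and (PP) dataset". It fixes the denominator as follows: "No. of subjects with embryo transfer = Subjects with embryo transfer attempted".

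**The concern.** The protocol and the SAP give incompatible instructions for the primary endpoint, and SAP section 7 contradicts itself. A statistician who follows the SAP reports two percentages with no test, no effect estimate and no interval. One who follows the protocol runs a stratified test that the SAP says will not be done.

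A reader could compare the arms crudely from the published counts. The pre-specified analysis, adjusted for the factors used in randomisation, would still be missing, and that analysis is what answers the trial's question. If the sponsor ran the protocol's test anyway, SAP section 4 might oblige the report to label it as unplanned, since analyses "not identified in this prospective IAP will be clearly identified in the CSR".

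The firm conflict is confined to the primary endpoint. For secondary endpoints, protocol 8.4.3 promises descriptive statistics and leaves further methods to the SAP.

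**Working it through.** **1. Protocol commitments against the SAP**

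| Protocol commitment | SAP |
|---|---|
| CMH test adjusted for site and age group (8.4.2; factors in 8.2) | No between-group comparison (7); absent from 14.1 |
| Odds ratio with 95% CI (8.4.2) | No confidence intervals (7); absent from 14.1 |
| Logistic model (8.4.2, 6.11) | No regression models (7) |
| Two-sided 0.05, 80% power (8.1) | No test to which these apply |

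SAP 14.4 lists no exploratory analysis, so the test does not return there. The SAP's references cite protocol version 3.0 of 31 January 2018, the version reviewed here, so no later protocol in these documents explains the removal. The SAP's modification history says only that versions followed client comments or suggestions. It does not show which version introduced the cancelling sentences.

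**2. The plan's sample size**

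Inputs (protocol 8.1): p1 = 0.30; p2 = 0.30 × 1.25 = 0.375; two-sided alpha 0.05; power 0.80. Mean rate = 0.3375.

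n = [1.96 × √(2 × 0.3375 × 0.6625) + 0.8416 × √(0.30 × 0.70 + 0.375 × 0.625)]² / 0.075²

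= (1.3107 + 0.5610)² / 0.005625 = 622.8, so 623 per arm.

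Drop-out: 623 / 0.90 = 692.2, so 693 per arm and 1,386 in total. Power at 623 per arm is 80.0%. The plan's figures reproduce exactly.

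**3. What the planned analysis would show (crude approximation, 623 per arm)**

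- Smallest significant difference with control at 30%: d = 1.96 × √(2 × pbar × (1 − pbar) / 623), with pbar = 0.30 + d/2. This gives d = 0.0521, that is 30% versus 35.2%.
- Odds ratio at the design rates: (0.375/0.625) / (0.30/0.70) = 1.40.
- SE of log OR = √(1/186.9 + 1/436.1 + 1/233.6 + 1/389.4) = 0.1204. The 95% CI is exp(0.3365 ± 1.96 × 0.1204) = 1.11 to 1.77.

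**4. Does stratification change this?**

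A CMH test was simulated over 32 strata (16 sites × 2 age groups), with 4,000 runs per setting and 624 per arm. Equal sites, a 65/35 age split and the site and age effects are assumptions; the 30% control rate and the 16 sites come from the protocol.

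| Site SD, age OR (assumed) | Power | Mean OR (mean 95% CI) | Type I error |
|---|---|---|---|
| 0, 1.0 | 78.3% | 1.394 (1.101 to 1.765) | 4.9% |
| 0.3, 0.7 | 79.8% | 1.404 (1.105 to 1.784) | 5.0% |
| 0.5, 0.6 | 77.7% | 1.401 (1.098 to 1.788) | 4.7% |

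The crude figures are close to the stratified ones.

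**5. The denominator (separate from the cancellation, but needed for a restored test)**

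The Full Analysis set is all randomised subjects (SAP 8.2). The rate divides by subjects with embryo transfer (protocol 8.4.2, SAP 14.1), which comes after Day 1 randomisation (protocol 6.7). Take 693 randomised per arm and count subjects without transfer as not pregnant. The no-transfer rates below are assumed, as the documents give none.

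| No transfer, control / GERI+ | Rates, all randomised | Power, all randomised | Power, per transfer |
|---|---|---|---|
| 10% / 10% | 27.0% vs 33.75% | 78% | 80% |
| 8% / 12% | 27.6% vs 33.0% | 59% | 80% |
| 12% / 8% | 26.4% vs 34.5% | 91% | 80% |

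For example, in the second row: 0.30 × 0.92 = 0.276 and 0.375 × 0.88 = 0.330.

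**The case against.** **The change is disclosed.** The sentence claiming no changes is followed at once by a qualification, in the right section, so it can be read as adopting the protocol's methods with exceptions. That is fair: nothing is hidden. But the exceptions remove the whole confirmatory analysis, and none is explained.

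**The protocol leaves details to the SAP.** It does, for the model and analysis. Specifying details does not extend to abolishing the test.

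**A reason may exist elsewhere.** Some front pages of the SAP were not available for review, so the statement that no reason is given covers the visible text only. No motive, and nothing about timing, should be inferred from the version log.

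**The size is illustrative.** This stands. The documents give no actual enrolment. SAP 8.2 allows the per-protocol set to be used if it exceeds 40% of the planned number, 0.40 × 1,386 = 554, or about 277 per arm. At that size the formula above gives power of about 46%. The figures in the working describe the design, not the data that will be obtained.

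**Restoring the test raises other questions.** This also stands, without defeating the point. Protocol 8.4.2 calls the logistic model a sensitivity analysis, while 6.11 ties it to testing the primary endpoint. The 6.11 covariates include number of embryos transferred, which is determined after randomisation, and luteal phase support, which is recorded at the hCG visit. SAP 14.1 says that the endpoint includes ectopic pregnancy but derives it from intrauterine pregnancies only.

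**An amendment may come too late to matter.** Last patient in was planned for December 2019, before SAP 2.0 of 14 January 2020, so withdrawing the power statement would change no conduct. It would still make the protocol agree with the analysis actually planned.

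**Conclusion.** The concern holds and must be fixed. Followed as written, the SAP leaves a trial of 1,386 subjects, sized for a two-sided 0.05 test at 80% power, without its primary test, odds ratio, confidence interval or sensitivity model. The sample size itself is correct.

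The contradiction rests on the text alone and needs no assumption. The size figures assume the design rates and full enrolment, and the simulation and denominator powers also use the assumed inputs labelled above.

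**What to change.** Reconcile the documents before database lock, by one of two routes.

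**Option A: keep the confirmatory trial.**

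- Delete the two cancelling sentences from SAP section 7.
- Write into SAP 14.1 the CMH test stratified by site and age group (18-35, 36-40), two-sided 0.05, with the common odds ratio and 95% CI.
- Add the protocol's logistic sensitivity model. State its role, so that protocol 8.4.2 and 6.11 agree, and list its covariates, marking those determined or recorded after randomisation.
- Name one denominator as primary, all randomised or subjects with embryo transfer, and show the other.
- Make the ectopic-pregnancy wording and the derivation in SAP 14.1 agree.

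Cost: SAP wording and a few lines of SAS code; no new data and no new patients.

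**Option B: make the trial descriptive.**

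- Record this in SAP section 7 as a change, with its reason.
- Withdraw the test and the 80% power claim through a written amendment under protocol 10.6.
- Make no superiority statement in the report.

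Cost: SAP wording plus the amendment, with ethics committee submission if it is substantial.

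Under either route, restore the Subgroup Analysis set of protocol 8.3, which SAP 8.2 omits, or list its removal in SAP section 7.

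SAP 6.2 bars database lock and unblinding until the plan is approved. SAP 2.0 is dated 14 January 2020, and last patient off study was planned for March 2020. By that calendar either route could be completed before lock; actual dates are not in the documents.

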# **8** Protocol Deviations and Analysis Sets

#### 8.1 Definition of Protocol Deviations

The definition of the major and minor protocol deviations are as follows.

Major protocol deviations are:

- 1. The number of 2PNs is less than 4 or missing
- 2. Subject is not randomized or not treated as randomized
- 3. Technical issues with GERI which are not reported as device deficiency
- 4. EEVA test applied to Poor Quality embryos instead of standard morphology
- 5. Control arm- Embryos with optimal cell number and grade were NOT transferred

All other deviations will be counted as minor deviations.

#### 8.2 Definition of Analysis Sets and Subgroups

#### **Full Analysis (FA) dataset:**

(FA) dataset includes all randomized subjects. Subjects will be presented as randomized.

#### Per Protocol (PP) dataset:

(PP) dataset is defined as:

Subjects, who completed the study without major protocol deviation, and:

- For subject randomized Geri+ group:
  - o embryos are cultured to Day 3, and are assessed by Eeva per Eeva IFU, or by standard morphology if this subject only has poor quality embryos;
  - embryo(s) with the highest Eeva score (for subjects with good and fair quality embryos), or best morphology grade (for subjects with poor quality embryos only, or with poor quality embryos and no more than one good/fair quality embryos) is/are transferred on Day 3 of embryo culture;
- For subjected randomized to Control group:
  - Embryos are cultured to Day 3, and the embryo(s) with the optimal cell number and grade is/are transferred.

Major protocol deviations are defined in section 8.1

The FA population is the primary analysis population.

PP population is used for sensitivity analysis. PP population will be considered only if it is less than 90% of FA population and more than 40% of total planned number of subjects.

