6.10 Definition of Completion of the Study

Completion of the study is achieved when all subjects finish the test for ongoing pregnancy.

The subject may complete and exit from this trial at the following time points:

- Test for hCG 12-18 days post embryo transfer: a subject will exit from the trial if the blood or urinary test result for hCG is negative. Otherwise subject waits until the test for clinical pregnancy.
- Test for clinical pregnancy at gestational weeks 6-8: a subject will exit from the trial if the ultrasound test result for clinical pregnancy is negative. Otherwise the subject waits until the test for ongoing pregnancy.
- Test for ongoing pregnancy at gestational weeks 10-12: a subject will finish the

Protocol Version: 3.0 / Jan 31, 2018 24 / 49

trial

trial at this time point, regardless of whether the ultrasound result for ongoing pregnancy is positive or negative.

 Miscarriage: a subject will exit from the trial upon spontaneous or therapeutic miscarriage.

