7.4 Data Collection on Day of hCG Test

A standard urine or blood serum hCG test is performed 12-18 days after embryo transfer, following the routine practices at the trial site. The following information is recorded in the LPS (Luteal Phase Support) and Clinical Outcome eCRF:

- · Strategy of LPS;
- · Date of the hCG test;
- · Method of hCG test and the result;
- Quantitative β -hCG, as applicable.

If the result of the hCG test is negative, the subject will have completed the trial and be exited at that time (complete **Trial Exit eCRF**).

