7.5 Data Collection for Clinical Pregnancy Ultrasound Test

The ultrasound test to verify clinical pregnancy is carried out between gestational weeks 6 and 8. The following information is recorded in the LPS and Clinical Outcome eCRF:

- Date of the last ultrasound test for clinical pregnancy;
- Result
 - Number of intrauterine gestational sacs
 - Number of fetal heartbeats
 - Ectopic pregnancy (Yes or No)
 - Biochemical pregnancy (Yes or No)
 - Other

If the result of the ultrasound test is negative, that is, if no fetal heartbeat is detected, then the subject will have completed the trial and be exited at that time (complete **Trial Exit eCRF**).

Protocol Version: 3.0 / Jan 31, 2018 27 / 49

trial

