8.3 Analysis Sets

Three analysis sets will be used: the Full Analysis dataset, the Per Protocol dataset and the Subgroup Analysis dataset.

- Full Analysis (FA-) dataset includes all randomized subjects. Subjects will be presented as randomized.
- Per Protocol (PP) dataset includes all subjects who have been treated according to the Clinical Trial Protocol and have received Day 3 fresh embryo transfer, with no major Clinical Trial Protocol violation in respect of factors likely to affect the efficacy of treatment.
- · Subgroup Analysis dataset (SA):Subjects who had embryos transferred which were either good or fair (i.e. not poor quality)

32 / 49

trial

• .

The FA population is the primary analysis population. PP population is used for sensitivity analysis. SA population is used for supportive analysis.

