#### 10 Trial Subjects

#### 10.1 Disposition of Subjects and Discontinuations

A table with

- Number of subjects screened
- Number of subjects with screen failure
- Number of subjects enrolled in the study
- Number of subjects randomized in the study
- Number of subjects in Full Analysis (FA) dataset
- Number of subjects in Per Protocol (PP) dataset
- Number of subjects completed the study as per protocol
- Subject completed the study as per protocol and appropriate outcome (Failed to conceive/ Biochemical pregnancy/ Spontaneous Miscarriage/ Clinical pregnancy/ Ongoing pregnancy/ Subject underwent therapeutic abortion/elective abortion)
- Number of subjects who discontinued from the study
- Subject did not complete the study as per protocol and appropriate outcome (Fresh embryo transfer was cancelled/ Subject requested to be withdrawn after embryo transfer/ Investigator withdrew subject/ Imaging was discontinued prior to completion/ Subject was lost to follow-up/ Subject was non-compliant/ Other)
- Fresh embryo transfer was cancelled, appropriate reason (No cleavage/ No viable embryo for transfer/ Freeze all due to elevated risk of OHSS/ Other)

will be summarized as number and percentage for both the treatment groups and overall.

Subjects Screened are the subjects for whom "Date informed consent signed by subject/partner" is available.

Subjects enrolled in the study are the subjects who satisfy both the inclusion and exclusion criteria.

Screen failure subjects are the subjects who are screened but not satisfying any one of the inclusion or exclusion or both criteria.

Listing will be provided for details of randomized subjects from (FA) dataset.

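### The SAP's per-protocol set requires study completion, which comes later for heartbeat-positive women, so exits after the week 6-8 scan remove known primary events; the net direction of bias is not fixed

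*SAP*

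**What the plan says.** **PP membership.** Protocol 8.3 defines the set by treatment: it "includes all subjects who have been treated according to the Clinical Trial Protocol and have received Day 3 fresh embryo transfer", without a major violation likely to affect efficacy. SAP 8.2 starts from a different condition, "Subjects, who completed the study without major protocol deviation, and", and then adds arm-specific culture, assessment and transfer requirements. SAP 7 reports no change to the planned analyses. The exceptions it goes on to name (no group comparison, confidence intervals or regression) do not include the PP set.

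**Completion.** Protocol 6.10 opens with "Completion of the study is achieved when all subjects finish the test for ongoing pregnancy" and then lists the points at which an individual woman may complete and exit. Protocol 7.4: "If the result of the hCG test is negative, the subject will have completed the trial and be exited at that time". Protocol 7.5: "if no fetal heartbeat is detected, then the subject will have completed the trial". Under 6.10 and 7.6, a woman with a heartbeat goes on to the week 10-12 scan unless she miscarries first.

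**Non-completion.** SAP 10.1 counts withdrawal after transfer as not completing, together with "Subject was lost to follow-up/ Subject was non-compliant/ Other". Its list of completed outcomes contains clinical pregnancy as an item separate from ongoing pregnancy.

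**Role of PP.** It is a sensitivity set, considered only if it is below 90% of the full analysis (FA) set and above 40% of the planned number of subjects (SAP 8.2).

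**The concern.** The primary outcome is settled by the week 6-8 scan at the latest. Under the SAP rule, PP membership for a woman with a heartbeat depends on what happens afterwards, whereas a woman with a known negative result has already completed. Membership is thus conditioned on follow-up after the outcome, and that follow-up is required only of women with the event.

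The rule also sits badly with two other protocol provisions. Protocol 6.7 and 8.1 define a drop-out as a randomized woman without primary endpoint data, so a woman lost after a positive scan is not one. Protocol 6.9 keeps data up to the withdrawal of consent.

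What is at stake is how PP is read against FA. SAP 7 removes tests and models, so the heartbeat rate in FA and PP (SAP 14.1) is the main sensitivity comparison left for the primary endpoint. A gap could be taken for an effect of adherence when part of it comes from the set definition. The PP implantation rates (SAP 14.2.4) would lose the same heartbeat-positive sacs.

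**Working it through.** **1. The plan's own figure.** Inputs from protocol 8.1: control 30%, relative increase 25% (so 37.5%), two-sided alpha 0.05, power 80%, drop-out 10%. With the pooled-variance formula, mean rate 0.3375:

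n = [1.960 × √(2 × 0.3375 × 0.6625) + 0.842 × √(0.30 × 0.70 + 0.375 × 0.625)]² / 0.075² = 622.8, so 623 per group.

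623 / 0.90 = 692.2, so 693 per group and 1,386 in total. The stated figures reproduce.

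**2. Who leaves PP through the completion condition.**

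| Last known status | Completed? | Effect of the SAP rule |
|---|---|---|
| hCG negative | Yes, at 12-18 days | stays |
| No heartbeat at weeks 6-8 | Yes, at that scan | stays |
| Heartbeat, then miscarriage | Yes, at miscarriage | stays |
| Heartbeat, then lost or withdrawn | No under protocol 6.10 | a known event is removed |
| Lost between transfer and a known outcome | No | a woman counted as a non-event in FA is removed |

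The last row follows from SAP 14.1, where the denominator is all women with transfer attempted, and SAP 9, where missing data are not imputed. A rare exception to the pattern is an ectopic pregnancy with a heartbeat: SAP 14.1 counts heartbeat-positive cases among intrauterine pregnancies only, so she could be a known non-event who has not yet completed.

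**3. Late loss alone.** Let L be the share of heartbeat-positive women who exit after the week 6-8 scan without miscarriage. L is assumed. The 10% drop-out figure cannot supply it, because that figure covers only women without primary endpoint data.

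PP rate = p(1 − L) / (1 − pL). The odds in each arm are multiplied by (1 − L), so the odds ratio is multiplied by (1 − L for GERI+) / (1 − L for control).

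| L control | L GERI+ | PP rates | Difference (points) | Odds ratio |
|---|---|---|---|---|
| 0 | 0 | 30.0% vs 37.5% | 7.5 | 1.40 |
| 2% | 2% | 29.6% vs 37.0% | 7.5 | 1.40 |
| 5% | 5% | 28.9% vs 36.3% | 7.4 | 1.40 |
| 10% | 10% | 27.8% vs 35.1% | 7.2 | 1.40 |
| 0 | 5% | 30.0% vs 36.3% | 6.3 | 1.33 |
| 5% | 0 | 28.9% vs 37.5% | 8.6 | 1.47 |

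Events removed with 623 women per arm are 623 × p × L. At L = 5% that is 9.3 control and 11.7 GERI+ events, out of 186.9 and 233.6 expected. With no true effect (30% in both arms), a 5% late loss in one arm only gives an odds ratio of 0.95 or 1.05.

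**4. Adding early loss.** Let m be the share of transferred women lost before their outcome is known, assumed independent of outcome. The FA rate is p(1 − m), because these women count as non-events. At m = 5% it is 28.5% vs 35.6%. With L = 5% as well, the SAP's PP rate is 28.9% vs 36.3%, which is above FA. The two losses cancel when m = L(1 − p) / (1 − pL). At L = 5% that is 0.035 / 0.985 = 3.6% in control and 0.03125 / 0.98125 = 3.2% in GERI+. The sign of the PP minus FA gap therefore turns on two rates that the documents do not give.

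**The case against.** The strongest counter-argument is that the deletion is not certain. SAP 10.1 lists clinical pregnancy among completed outcomes, so a woman last seen at weeks 6-8 could be coded as a completer and stay in PP. That stands as an ambiguity. It does not settle the matter, because protocol 6.10 and 7.6 take a heartbeat-positive woman on to weeks 10-12, and SAP 8.2 does not say which reading applies.

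It is also fair that the consequence is limited. FA is the primary set and is untouched; PP is used only within its size limits; no formal contrast is planned; equal late loss leaves the odds ratio alone; subjects are blinded. SAP 10.1 and 10.2.2 tabulate non-completion and PP exclusions by arm, so the exclusions would be partly visible. Neither section says that they will be split by primary outcome, so the cause of a gap would not be evident from those tables. Clinicians are not blinded, so unequal late loss cannot be ruled out, but nothing in the documents shows it.

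A reader might infer that the completion rule removes only successes and so biases PP downward in both arms. The documents do not support that. The statement about successes applies to exits after the week 6-8 scan. The same rule removes women lost earlier, which raises the PP rate relative to FA. Nor does the 10% drop-out allowance make a late loss of that size likely.

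**Conclusion.** The point holds in limited form. SAP 8.2 adds an undeclared condition that the protocol's PP set lacks, and meeting it depends on the primary outcome. Exits after the week 6-8 scan remove known events and essentially no known non-events. Taken alone, this lowers the PP rate by 1.1 points in control and 1.2 in GERI+ at an assumed 5% late loss, without moving the odds ratio of 1.40. A 5% loss in one arm only moves it to 1.33 or 1.47.

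These sizes rest on the planning rates and on assumed late-loss rates. The net direction against FA is not fixed, because early losses act the other way, and the reach of the rule depends on how SAP 10.1 is read. The primary analysis is not affected. The change is still worth making: PP should not depend on what happens after the outcome is known.

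**What to change.** In SAP 8.2, replace the completion condition with this: the woman received a Day 3 fresh embryo transfer and has a known primary outcome, meaning a negative hCG test or a week 6-8 scan result, including a documented pregnancy loss before the scan. Keep the exclusion for major protocol deviations and the arm-specific conditions. State that exit after the primary outcome is known is not a reason for exclusion from PP. Declare in SAP 7 how this differs from protocol 8.3.

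Simply deleting the completion condition is not enough. Women with an unknown outcome would then enter PP and count as failures: at m = 5%, 28.5% vs 35.6%.

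The cost is a short text change and one programming condition, using data already collected. Some PP women will have no week 10-12 result and will appear as missing for ongoing and multiple pregnancy, which SAP 9 already provides for. hCG-positive women lost before the scan remain outside PP, so their number should be shown by arm.
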